Official Study Title:

Impact of Sodium-Glucose Co-transporter 2 inhibitors on Cardiovascular System and Anemia in Non-diabetic Chronic Kidney Disease Patients. A Randomized-Controlled Clinical Trial

ClinicalTrials.gov Identifier (NCT Number):

Pending

Document Type:

[Study Protocol / Statistical Analysis Plan]

Document Date:

[April 24, 2022]

Sponsor/Collaborator:

Mansoura Urology and Nephrology Center, Mansoura University, Egypt

Principal Investigator:

[name], MD, PhD

Introduction

Chronic kidney disease (CKD) affects approximately 10% of the adult population worldwide (1). The most common causes of CKD are diabetes, hypertension, and chronic glomerulonephritis (2). Treatment for CKD includes angiotensin converting enzyme inhibitor (ACE-I) / angiotensin II receptor blockers (ARBs), lipid and blood pressure (BP) control (3).

Sodium-glucose co-transporter 2 inhibitors (SGLT2i) are a newly approved class of oral anti-diabetic agents that increase the urinary excretion of glucose, thereby lower blood glucose levels, weight, and blood pressure (4).

There is growing evidence indicating that SGLT2 inhibition is reno-protective. This effect is thought to be achieved partly by mechanisms independent of lowering blood glucose levels (5), such as reduced intra-glomerular pressure through an enhanced tubule-glomerular feedback mechanism (6-7), reduced glucose and sodium transport over the proximal tubular cells (8), increased natriuresis (9) and reduced systemic BP (10-11).

A recent clinical trial (**DAPA-CKD**) showed that SGLT2i treatment reduced the risk of worsening kidney function or death from cardiovascular or kidney disease in patients with chronic kidney disease with and without type 2 diabetes (12).

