Dapagliflozin which was originally developed to control blood glucose level in patients with diabetes has recently been shown to have beneficial effects on both the heart and kidney.

Importantly, a large clinical trial has shown dapagliflozin reduced kidney problems. From the way we think the pills work, there is good reason to believe this new medication could benefit people who have kidney disease even they are not diabetic.

To date, there hasn't been a trial that studied the effect of dapagliflozin in terms of anemia improvement only on non-diabetic CKD.

Objectives

The main objective of this study is to:

- Compare use of SGLT2i versus placebo and standard care in regression of chronic kidney disease in non-diabetic CKD patients.
- Study the effect of SGLT2i in decreasing the risk of anemia and improving anemia in non-diabetic CKD patients.
- Study the impact of SGLT2i regarding cardiovascular system.

Hypothesis

Additional therapies to slow kidney function decline are highly desired. The DAPA-CKD trial demonstrated that the sodium glucose co-transporter 2 inhibitor dapagliflozin significantly reduced the risk of kidney failure and prolonged survival in participants with chronic kidney disease with and without type 2 diabetes.

Patients and methods

Study sitting: Urology and Nephrology Center, Mansoura University.

Study design and sample size:

- **Sample size:** was calculated based on previous research by (DAPA-CKD) by (Heerspink et al., 2020) using G. power program with α error 0.05 and power 80% and it was equal to approximately 98 patients.

Type of the study: Randomized controlled trial.

Patients' enrollment: 100 patients with non-diabetic CKD with an estimated glomerular filtration rate (eGFR) of 20-75 ml/min/1.73m² will be randomized into 2 equal groups:

- **Study group:** 50 patients will receive SGLT2i as add on drug, Dapagliflozin 10 mg will be used once daily with or without food.
- **Control group:** 50 patients will receive placebo beside the conventional medications.

All patients will be followed-up for 12 months and their results will be interpreted.

Inclusion criteria:

1. Non-diabetic CKD patients aged more than 18 years.
2. Patient with eGFR > 20 ml/min/1.73m² by 2021 CKD-EPI creatinine equation

Exclusion criteria:

1. eGFR < 20 ml/min per 1.73 m².
2. Medical history of chronic disease (diabetes mellitus, chronic liver disease, bladder cancer, severe respiratory distress).

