3. Evidence of urinary obstruction or difficulty in voiding at screening.
4. Receiving high dose diuretics or combined ACEI and ARB.
5. History of recurrent urinary tract infection.

6. Active infection including TB and HIV.
7. Current or previous organ transplantation or expected to get a kidney transplant within 12 months.
8. Patients who are on SGLT2i for more than the preceding 3 months.

Study design:

Study Protocol:

- Patients included in the study will be treated with dapagliflozin initiated at a single daily morning dosage of 10 mg/day.

Methods:

The following data will be collected and evaluated for all patients:

I-Baseline investigations:

- Patients of both groups will be subjected to full history taking including duration of CKD and drug history and routine clinical examination.
- Ankle/brachial pressure index (ABPI) to assess peripheral vascular disease.

➤ Laboratory investigations:

- 1) Serum creatinine, Creatinine clearance.
- 2) Urine analysis.
- 3) 24-hour urine protein and/or spot urine protein/creatinine ratio.
- 4) Random blood glucose.
- 5) Lipid profile
- 6) Iron profile tests:

- Hemoglobin
- Mean corpuscular volume (MCV) and Hematocrit (Hct).
- Serum ferritin
- Transferrin saturation (TSAT)
- Serum hepcidin level
- Serum erythropoietin level.

7) B-type natriuretic peptide (BNP) level.

➤ **Cardiovascular investigatory tools:**

- Electrocardiography (ECG).
- Echocardiography to assess myocardial function.

➤ **Radiological investigations:**

- Agatston score using CT scan: for assessment of coronary calcification.

1. II-Post-intervention investigations:

All patients will be evaluated every visit (every 3 months) regarding:

- Regular measurement of blood pressure each visit.
- Ankle/brachial pressure index.
- Laboratory investigations:
 - 1) Serum creatinine, creatinine clearance.
 - 2) Urine analysis.
 - 3) 24-hour urine protein and/or spot urine protein/creatinine ratio.
 - 4) Fasting blood glucose.
 - 5) Lipid profile.

6) Iron profile (Hemoglobin, MCV, hematocrit, ferritin, TSAT,)

All patients will be evaluated at 12 months regarding:

➤ Ankle/brachial pressure index.

➤ **Laboratory investigations:**

1) Serum creatinine, Creatinine clearance.

2) 24-hour urine protein and/or spot urine protein/creatinine ratio.

3) Urine analysis.

4) Fasting blood glucose.

5) Lipid profile.

6) Iron profile tests:

- Hemoglobin
- Mean corpuscular volume (MCV) and Hematocrit (Hct).
- Serum ferritin
- Transferrin saturation (TSAT)

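### In this placebo trial, the 3-monthly urine analysis is a likely cue to the arm, with no rule on who sees it, and no record of background drugs is planned after baseline

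*Combined protocol and SAP*

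**What the plan says.** All places are in the combined protocol and SAP.

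- **Control (Patients' enrollment):** "50 patients will receive placebo beside the conventional medications".
- **Design label:** "Type of the study: Randomized controlled trial". No masking term is attached. The Study Protocol block describes only the active drug: "Patients included in the study will be treated with dapagliflozin initiated at a single daily morning dosage of 10 mg/day".
- **Drug effect (Introduction):** the class is said to "increase the urinary excretion of glucose, thereby lower blood glucose levels, weight, and blood pressure (4".
- **Population (Exclusion criteria, item 2):** "Medical history of chronic disease (diabetes mellitus, chronic liver disease, bladder cancer, severe respiratory distress" is an exclusion, so patients with diabetes do not enter.
- **Visits (Post-intervention investigations):** "All patients will be evaluated every visit (every 3 months) regarding", followed by a list that includes blood pressure, urine analysis, fasting blood glucose and the iron profile with hemoglobin and hematocrit. The 12-month list repeats urine analysis and adds ECG, echocardiography and CT.
- **Background drugs:** two entry-stage items bear on them. Exclusion 4 is "Receiving high dose diuretics or combined ACEI and ARB", and the baseline work-up includes "full history taking including duration of CKD and drug history and routine clinical examination". Neither the 3-monthly nor the 12-month list includes medication.

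**The concern.** A placebo protects a comparison only as far as the people who treat, report and read outcomes stay unaware of the arm. Here the plan's own pharmacology and visit schedule work against that. In a patient without diabetes, urine glucose on a routine report points to dapagliflozin, and repeated negative reports point to placebo. The same visit supplies a blood pressure reading, which is a natural occasion to adjust other drugs.

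The outcomes most exposed are secondary. Echocardiography involves reader judgement, and hypoglycemia episodes and serious adverse events depend on reporting. ACEI/ARB, diuretics and other antihypertensives act on eGFR and, through volume, on hematocrit and ventricular loading. Iron and erythropoietin-type drugs act directly on the anemia measures. The cardiovascular system and anemia are the subjects in the trial's title.

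The missing drug record matters even with perfect masking. The Introduction says the class lowers blood pressure, so background doses could drift apart by arm for ordinary clinical reasons, and the plan collects nothing that would describe this.

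**Working it through.** The plan gives no figure on this point to reproduce. The check is a reading of the schedule, then an illustration of scale.

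**1. How often the cue appears.** Months 3, 6 and 9 fall before the 12-month readings: 3 reports x 50 patients = 150 per arm, and 3 x 100 = 300 in all. The 12-month visit adds one more per patient.

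**2. What the route to bias needs.**
- Documented: a placebo control, a drug class that raises urinary glucose, patients without diabetes, recurring urine analysis, and no rule on who sees the result.
- Assumed: staff are meant to be masked, the report includes a glucose line, staff see it and infer the arm, and they then treat or read differently.

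**3. Illustration for eGFR.** The Statistical Analysis section names an unpaired t-test. Take 12-month eGFR, 50 per arm, no true effect, two-sided 5% level, 98 df.
- Assumed effect of one drug change: 3 to 5 ml/min/1.73m², always in the same direction.
- Assumed difference between arms in the share of patients changed because of an inferred arm: 10 to 20 points.
- Shift = effect x difference in share: 3 x 0.10 = 0.3 up to 5 x 0.20 = 1.0; the middle is 4 x 0.15 = 0.6.
- If a third of the changes go the other way, the net factor is 2/3 - 1/3 = 1/3, and the shift is 0.1 to 0.33.
- SD: an even spread over the eligible 20-75 gives 55/√12 = 15.9. SDs of 10 and 20 are taken as a range.
- SE = SD x √(2/50). Noncentrality = shift/SE. Detectable difference at about 80% power = 2.80 x SE.

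| | SD 10 | SD 15.9 | SD 20 |
|---|---|---|---|
| SE | 2.0 | 3.18 | 4.0 |
| Detectable difference | 5.6 | 8.9 | 11.2 |
| False-positive rate, shift 0.1 | 5.03% | 5.01% | 5.01% |
| shift 0.3 | 5.25% | 5.10% | 5.06% |
| shift 0.33 | 5.31% | 5.12% | 5.08% |
| shift 0.6 | 6.02% | 5.40% | 5.25% |
| shift 1.0 | 7.85% | 6.12% | 5.70% |

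At SD 15.9 the shift is 0.3/8.9 = 3% to 1.0/8.9 = 11% of the detectable difference. The plan states no change-score analysis, so none is computed. The documents give no basis for a figure on hematocrit, echocardiography or adverse events.

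**4. Primary composite.** A 50% decline means a fall of 10 from an eGFR of 20 and 37.5 from an eGFR of 75. Assumed drug effects of 3 to 5 fall well short of that. The end-stage kidney disease component is not defined and could depend on a clinician's decision, so this reasoning does not cover it.

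**5. What a drug table could show.** For 20% v 30% of patients changed, the 95% half-width is 1.96 x √(0.2 x 0.8/50 + 0.3 x 0.7/50) = 0.169, about ±17 points.

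**The case against.** The best case against is that the chain from cue to bias is long and mostly assumed. Nothing in the documents says that the urine report includes glucose, that treating staff act on it, or that echocardiography or CT readers receive it. The eGFR inputs are invented, and even so the distortion is small: the 7.85% figure needs the largest shift, every change in one direction and an SD well below that of an even spread. For the outcomes closest to the title, no figure can be offered. All of this stands, and it limits the weight of the bias argument.

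It also stands that three stronger readings go too far.
- **That the trial is unmasked.** The documents do not say so. A placebo suggests that at least patients are masked. The Study design heading above the Study Protocol block has no text beneath it, and title and consent pages are not in the available copy, so wording on masking may exist there.
- **That drug changes will go unrecorded and undetected.** The documents show only that no recording is planned. Notes at this single center may hold some of the data.
- **That the eGFR or primary result is materially biased.** The figures above do not support it.

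The objection leaves the schedule itself untouched. The cue follows from the plan's own statements, and the visit lists contain no medication item. Both can be remedied at visits that already take place.

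**Conclusion.** The point holds as a should-fix design matter, with medium confidence. Two things are firm: the schedule gives a likely cue to the arm in a placebo trial with no rule on who sees it, and no collection or tabulation of background drugs is planned after baseline. Whether bias follows is conditional on staff masking being intended and on urine glucose being reported and seen.

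The size and sign of any bias cannot be derived from the documents. For the 12-month eGFR test, the illustrative false-positive rate is 5.1-6.1% at SD 15.9, 5.1-7.9% over SDs of 10 to 20, and 5.0-5.3% if a third of changes go the other way. Little effect is expected on the 50%-decline component of the primary outcome. What remains is an unquantified exposure of the secondary anemia, echocardiographic and reported safety outcomes, and an inability to describe co-treatment by arm from planned data.

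**What to change.** 1. **Study Protocol block:** state that patients, treating staff and the readers of echocardiography, ECG and CT are masked to allocation. After baseline (months 3, 6, 9 and 12), have the laboratory withhold the urine-glucose line from reports sent to them. Keep fasting blood glucose visible for safety.
2. **Post-intervention investigations and the 12-month list:** at each visit, record ACEI/ARB, diuretic, other antihypertensive, iron and erythropoietin-type drugs, with dose and the date of and reason for any change. Tabulate starts, stops and dose changes by arm. Background care otherwise stays with the clinician.

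**Cost:** a slightly altered laboratory report and a few fields on the visit form, with no extra test, visit or patient. The trial is unfunded, so the laboratory's ability to suppress one line should be confirmed first; the drug record does not depend on it.

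**Limits:** masking protection is partial, because hematocrit, hemoglobin and blood pressure are read at the same visits and remain weaker cues. With about ±17 points of uncertainty at 50 per arm, the drug table describes imbalance and does not test it.

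### Pregnancy and breast-feeding are neither excluded nor tested for, although every patient is scheduled for two CT scans and half are assigned dapagliflozin: a patient-safety gap in the eligibility criteria.

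*Combined protocol and SAP*

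**What the plan says.** Under Inclusion criteria the combined protocol and SAP sets two conditions. The first is "Non-diabetic CKD patients aged more than 18 years". The second is an eGFR above 20 ml/min/1.73m² "by 2021 CKD-EPI creatinine equation". Neither refers to sex, childbearing potential or contraception, and there is no upper age limit.

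The Exclusion criteria are numbered 1 to 8 without a gap or redaction. They cover low eGFR, listed chronic diseases, urinary obstruction, certain concomitant drugs, recurrent urinary infection, active infection, transplantation and prior SGLT2i use. The last item is "Patients who are on SGLT2i for more than the preceding 3 months". Item 7 excludes patients partly on an event foreseen during follow-up: "Current or previous organ transplantation or expected to get a kidney transplant within 12 months".

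Under Methods, the baseline section opens with "The following data will be collected and evaluated for all patients". Its laboratory list has seven items, ending with "B-type natriuretic peptide (BNP) level". The radiological item is "Agatston score using CT scan: for assessment of coronary calcification", and the same item appears in the 12-month evaluation, which also applies to all patients. The treatment text assigns 50 patients to daily dapagliflozin and 50 to placebo. Follow-up is 12 months.

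**The concern.** Eligibility criteria decide who may be exposed to what the protocol imposes. Here it imposes CT on everyone for research purposes and a study drug on half the patients. A trial with those two exposures should state its position on pregnancy and breast-feeding, and this one does not. Nothing later in the document closes the gap: no pregnancy test is listed at any visit, and the safety outcome names only hypoglycaemia and serious adverse events.

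What is at stake is avoidable exposure of a fetus to radiation and to a study drug and, for a breast-feeding woman in the study group, exposure to the drug while nursing. The documents give no data on the size of these risks. The point rests on the ordinary precaution that such exposure should be ruled in or out deliberately, not left unstated.

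**Working it through.** The plan gives no figure on this point, so there is none to reproduce. The check is a reading of the criteria and visit lists, followed by simple counts.

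**1. Does any criterion address pregnancy?**

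| Place | Items | Mention pregnancy, breast-feeding or contraception |
|---|---|---|
| Inclusion criteria | 2 | 0 |
| Exclusion criteria | 8 | 0 |
| Baseline laboratory list | 7 | 0 (no pregnancy test) |
| Three-monthly laboratory list | 6 | 0 (no pregnancy test) |
| 12-month laboratory list | 6 | 0 (no pregnancy test) |

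The unbroken numbering of the exclusion list shows that the omission does not come from reading the PDF.

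**2. What exposure does the protocol schedule?**

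- CT scans per patient: 1 at baseline + 1 at 12 months = 2, in both groups. For 100 patients, 100 × 2 = 200 scans.
- Dapagliflozin: 50 of 100 patients. Twelve months is the stated follow-up; the treatment duration is not stated separately.

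**3. How many patients might this concern?** The documents give no age or sex distribution. Assume 10 to 25 women of childbearing age among the 100.

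- Scans without a pregnancy check: 10 × 2 = 20 to 25 × 2 = 50.
- Expected number in the study group under equal allocation: 10/2 = 5 to 25/2 = 12.5.

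**4. How far could the results move?** Let k be the number of pregnancies in one arm of 50 and x the change in one affected patient's value. The shift in the arm mean is k × x / 50. The documents supply neither k nor x. Assume at most 2 pregnancies in the whole trial, changes of 10 to 40 ml/min/1.73m² in eGFR, and changes of 0.5 to 2 g/dL in haemoglobin.

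| Pregnancies in one arm | Shift in mean eGFR (ml/min/1.73m²) | Shift in mean haemoglobin (g/dL) |
|---|---|---|
| 1 | 1 × 10/50 = 0.2 to 1 × 40/50 = 0.8 | 1 × 0.5/50 = 0.01 to 1 × 2/50 = 0.04 |
| 2 | 2 × 10/50 = 0.4 to 2 × 40/50 = 1.6 | 2 × 0.5/50 = 0.02 to 2 × 2/50 = 0.08 |

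Even with both pregnancies in the same arm, the shift is at most 1.6 ml/min/1.73m² and 0.08 g/dL. With no pregnancy it is zero.

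**The case against.** **Other contacts would catch it.** This is a single-centre trial. Each patient has a history and clinical examination at baseline and is seen every three months. Ethics approval and written consent are recorded, and the consent pages, which are not in the text available, may carry a warning. This stands in part: it is too strong to say that a pregnant woman would be enrolled, or that nobody would notice. But none of these contacts is an eligibility criterion. History may reveal a pregnancy, yet no rule then makes the woman ineligible, and a baseline history cannot reveal one that begins before the 12-month scan.

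**The harm is not documented.** That is true. The documents contain nothing on fetal risk from CT or from dapagliflozin, and the numbers of women and pregnancies used here are assumptions without a source in the plan. The omission and the scheduled exposure are facts of the text; the size of the harm is not.

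**The transplant criterion proves nothing about pregnancy.** Agreed. It shows only that the list already has room for an event foreseen within follow-up.

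**Tests before the two scans leave the interval between them uncovered.** This also stands. The tests protect the scans. What happens if a pregnancy arises during treatment is a separate clinical rule for the sponsor and investigator to set.

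**Stronger readings to avoid.** A reader might infer that pregnancies would distort the eGFR and haemoglobin outcomes. The documents give no basis for this: on the assumed values the shifts in means are small, and no route to a false result on the primary outcome, a sustained eGFR decline of at least 50% or end-stage kidney disease, is shown. A reader might also infer that every patient takes the drug for 12 months. Only 50 are assigned to it, and the treatment duration is not stated.

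**Conclusion.** The gap is real and is one of patient safety. As the criteria stand, a pregnant or breast-feeding woman could be randomised and scanned, and in the study group could also receive dapagliflozin. The certain part is the text: 0 of 10 eligibility criteria address the matter, no pregnancy test is listed, and two CT scans are scheduled for each patient. The uncertain part is the frequency. It rests on an assumed 10 to 25 women of childbearing age and an assumed 0 to 2 pregnancies. On those figures any effect on the trial's means is likely small, and the analysis results are not the reason to act. The amendment should be made because the exposure is imposed by the protocol and is easily avoided.

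**What to change.** Add one item to the Exclusion criteria: pregnancy, breast-feeding, or pregnancy planned within the 12-month follow-up. For women of childbearing potential, add a urine pregnancy test to the baseline list and to the 12-month list, with the result known before the CT. Urine is already collected for urine analysis at both time points, so no new sample is needed. If enrolment has begun, the check before the 12-month CT can still be introduced.

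The protocol should also say who decides on management if a pregnancy arises during treatment; the content of that rule is for the sponsor and investigator.

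No change to the main analysis is needed. In particular, values measured during a pregnancy should not be set to missing: that would discard post-randomisation data for negligible gain, and the Statistical Analysis section has no method for missing values. At most, report a prespecified sensitivity analysis of the secondary outcomes without those measurements.

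The cost is one sentence, two low-cost tests per woman concerned (20 to 50 tests in all on the assumption above), and a few patients who become ineligible.

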Also, there are data suggesting SGLT2i acts by inhibiting hepcidin, which will increase iron bioavailability and red blood cell production (13). **Another mechanism is suggested via inducing medullary hypoxia which by turn increases the level of hypoxia inducible factor (HIF) and increase erythropoietin production (14).** These effects on erythropoiesis suggest that the use of SGLT2i reduces the occurrence of anemia. The post-hoc analysis of the CREDENCE trial found that the risk of anemia or the risk of starting anemia treatment in the anemia group of patients with type 2 diabetes and chronic kidney disease was significantly lower than that of the placebo group (15). According to the exploratory analysis of EMPA-REG test data, anemia improvement during SGLT2i treatment was closely related to beneficial cardiovascular outcomes (16).

Dapagliflozin, as a member of SGLT2i family, showed a beneficial effect on cardiovascular outcome (17, 18). As shown in many other trials, Other SGLT2 inhibitors have shown favorable cardiovascular effects, including a reduction in the risk

of hospitalization for heart failure, predominantly in patients with type 2 diabetes and established cardiovascular disease (19-21).

SGLT2 inhibition affects visceral adiposity, glycemic control, hyperinsulinemia, blood pressure, arterial stiffness, and albuminuria (22). Two mechanisms have been proposed as major drivers for beneficial cardiovascular outcome: the diuretic effect associated with SGLT2 inhibition with subsequent hemodynamic unloading of the left ventricle (23) and a shift in cardiac metabolism secondary to increased ketogenesis (24, 25).

Aim of the work

This study aims to:

1. Assess SGT2i role in delaying the progression of ongoing chronic kidney disease.
2. Investigate SGLT2i impact on anemia improvement among non-diabetic CKD patients.
3. Study the impact of SGLT2i on cardiovascular system in these patients.

Research questions

The main research question is: Does use of SGLT2i will show superiority over conventional lines of treatment of chronic kidney disease as regard to efficacy and safety?

Does the use of SGLT2i carry beneficial effect on anemia improvement among these patients?

Does the use of SGLT2i improve cardiac outcome in non-diabetic CKD patients?

Rationale and justification

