- Serum hepcidin level
- Serum erythropoietin level.

➤ **Cardiovascular investigatory tools:**

- Electrocardiography (ECG).
- Echocardiography to assess myocardial function.

➤ **Radiological investigations:**

- Agatston score using CT scan: for assessment of coronary calcification.

Outcomes:

Primary outcome measures:

- Time to the first occurrence of any of the components of the composite:
≥50% sustained decline in eGFR, reaching end-stage kidney disease.
[Time Frame: 12 months]

Secondary outcome measures:

- Effect of Dapagliflozin on eGFR.
- Effect of Dapagliflozin on anemia & erythropoietin level.
- Effect of Dapagliflozin on myocardial function and coronary calcifications.
- Safety of Dapagliflozin regarding the number of hypoglycemia episodes between groups and serious adverse events.

Statistical Analysis:

Qualitative data will be displayed in cross tabulations, and quantitative data will be described in terms of arithmetic mean \pm SD. Bivariate techniques will be used for initial evaluation of contrasts. Thus, the chi-square and Fisher's exact tests will be used for comparisons of frequencies of qualitative variables; the Mann-Whitney test and the unpaired t-test will be used for comparisons of means of two quantitative variables. A p-value ≤ 0.05 is considered significant. Patient survival rates will be assessed using the Kaplan-Meier method. All analyses will be carried out using the computer package SPSS for windows, release 21 SPSS Inc. Chicago, III, USA.

Administrative design

All the patients provided written informed consent before study entry and the approval was obtained from institutional review board (MS.22.04.1973) in Faculty of Medicine, Mansoura University. There is no funding.

References

1. Eckardt, K. U., Coresh, J., Devuyst, O., Johnson, R. J., Köttgen, A., Levey, A. S., & Levin, A. (2013). Evolving importance of kidney disease: from subspecialty to global health burden. *The Lancet*, 382(9887), 158-169.
3. Silver, S. A., Bell, C. M., Chertow, G. M., Shah, P. S., Shojania, K., Wald, R., & Harel, Z. (2017). Effectiveness of quality improvement strategies for the management of CKD: a meta-analysis. *Clinical Journal of the American Society of Nephrology*, 12(10), 1601-1614.

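### The eGFR outcome has no defined measure, and the unadjusted two-group tests available for it would mix any early fall in eGFR with later slope

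*Combined protocol and SAP*

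**What the plan says.** The first item under Aim of the work is "Assess SGT2i role in delaying the progression of ongoing chronic kidney disease". Under Outcomes, the secondary list contains "Effect of Dapagliflozin on eGFR" and nothing more: no value, change or slope, no visit, and no equation. The 2021 CKD-EPI creatinine equation is named only in the inclusion criteria.

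The Statistical Analysis section states that "the Mann-Whitney test and the unpaired t-test will be used for comparisons of means of two quantitative variables". It introduces its tests with "Bivariate techniques will be used for initial evaluation of contrasts", but no later analysis of a quantitative outcome follows. No baseline adjustment, slope or repeated-measures model appears.

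The data are richer than the analysis. Serum creatinine is measured at baseline, and then "All patients will be evaluated every visit (every 3 months) regarding" renal function among other items. Follow-up is fixed: "All patients will be followed-up for 12 months and their results will be interpreted". That gives post-baseline values at months 3, 6, 9 and 12; no visit before month 3 is listed.

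The Introduction offers, as one explanation of renal protection, "reduced intra-glomerular pressure through an enhanced tubule-glomerular feedback mechanism". It does not say what this does to eGFR in the first weeks.

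**The concern.** Delay of progression is a question about the rate of decline. If lower filtration pressure also reduces eGFR soon after the drug is started, a treated patient begins lower and then declines more slowly. A single comparison at month 12 adds these two parts, which have opposite signs. With only one year for the slope benefit to accumulate, the sum can be small, zero or negative while progression is truly slowed.

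The undefined outcome adds a second problem. A month-12 value, a change from baseline, a comparison at an earlier visit and a slope all fit the plan's wording. They can differ in sign, and nothing fixes the choice before results are seen.

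**Working it through.** The plan gives no expected eGFR effect, SD or early change, so there is no figure for this outcome to reproduce. Its one quantitative target, about 98 patients at alpha 0.05 and 80% power, comes without an effect size and cannot be rebuilt. It is not needed below.

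**Inputs from the documents:** 50 patients per arm; post-baseline visits at 0.25, 0.5, 0.75 and 1.0 year; 12 months of follow-up.

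**Assumed inputs (none in the documents):** early fall *f* of 0-4 mL/min/1.73m², complete by month 3; slope gain *g* of 1-3 per year, acting from the start; residual SD and slope SD each 3-4.

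**1. What each contrast estimates (dapagliflozin minus placebo)**

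- Month 12: g × 1 − f
- Month 3: g × 0.25 − f
- Slope, months 3 to 12: [(g − f) − (0.25g − f)] / 0.75 = g

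With g = 2:

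| Fall f | Month 3 | Month 12 | Slope 3-12 | Curves cross at 12f/g months |
|---|---|---|---|---|
| 0 | +0.5 | +2 | +2 | 0 |
| 1 | −0.5 | +1 | +2 | 6 |
| 2 | −1.5 | 0 | +2 | 12 |
| 3 | −2.5 | −1 | +2 | 18 |
| 4 | −3.5 | −2 | +2 | 24 |

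Any fall above zero makes the month-12 contrast smaller than the gain. It is zero when f = g and reversed when f > g. The month-3 difference is not the fall alone, because it already holds a quarter-year of slope gain.

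**2. What this does to a t-test on 12-month change**

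Take an assumed SD of change of 6. SE = 6 × √(2/50) = 1.2, and power for g = 2 by normal approximation is:

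- no fall: Φ(2/1.2 − 1.96) = 39% for benefit;
- fall of 2: net 0, so 2.5% for benefit;
- fall of 4: net −2, so under 0.1% for benefit and 39% for a significant result in the direction of harm.

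**3. A straight line from baseline does not solve it**

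For least squares on 0, 0.25, 0.5, 0.75 and 1.0 year, the mean time is 0.5 and the sum of squares is 0.625. A step of −f at every visit after baseline shifts the slope by −f × (−0.25 + 0 + 0.25 + 0.5)/0.625 = −0.8f. With f = 2 and g = 2 the fitted slope difference is 2 − 1.6 = 0.4. Baseline must therefore not enter as a response.

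**4. Precision**

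For months 3-12 the sum of squares of time is 0.3125.

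- Slope SE = √[(slope SD² + residual SD²/0.3125) × 2/50]. At SDs of 3: √(37.8 × 0.04) = 1.23. At SDs of 4: √(67.2 × 0.04) = 1.64.
- Unadjusted 12-month change SE = √[(slope SD² + 2 × residual SD²) × 2/50]. At SDs of 3: √(27 × 0.04) = 1.04. At SDs of 4: √(48 × 0.04) = 1.39.
- Detectable slope difference at 80% power (2.80 × SE): 3.4 to 4.6 per year.
- Power for a slope gain of 2: Φ(2/1.64 − 1.96) = 23% to Φ(2/1.23 − 1.96) = 37%.

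Widening the assumptions to residual SD 2-5 and slope SD 2-4 gives a slope SE of 0.82-1.96, a detectable difference of 2.3-5.5 per year, and power of 17-68% for a gain of 2.

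**The case against.** Several objections have force.

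- **The early fall is not in the documents.** A reader might infer that the protocol describes a fall in eGFR after starting the drug. It names reduced intraglomerular pressure as a protective mechanism and goes no further. The link to eGFR is physiologically plausible, but it is an assumption, as is its size. This stands.
- **The month-12 comparison is inferred.** A reader might take the plan to commit to it. The plan commits to no measure. A t-test at each visit, or on per-patient slopes, would fit the text, and the tests are called initial. This also stands, but it leaves the outcome undefined rather than protected.
- **A count of scenarios is not a probability.** With falls of 1-4 and gains of 1-3 in unit steps, 9 of 12 combinations are zero or negative, 3 of them exact ties. With falls of 0-3 it is 6 of 12; with 0-4 it is 9 of 15. These fractions reflect the grid and do not show that reversal is likely.
- **The total effect at 12 months is a legitimate target.** The Objectives section speaks of regression of kidney disease, for which the net level matters. A slope that ignores the early fall can flatter the drug. This stands, and is why the slope should not decide alone.
- **The primary outcome already serves the first aim.** A reader might conclude that composite events will be few and that eGFR will carry the renal conclusion. No event rate is given, so the documents do not settle this.
- **The slope estimate is weakly powered.** True, and it has to be stated with the proposal.

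None of this supplies a defined measure, a baseline adjustment or a use for the 3-monthly values.

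**Conclusion.** The point holds in conditional form. What the documents establish is that the eGFR outcome is undefined and that the only methods available for it are unadjusted two-group tests, although baseline and quarterly creatinine are collected and the first aim is delay of progression.

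The distortion depends on two conditions: that month-12 eGFR or its change is compared, and that an early fall occurs. If both hold, the contrast is too small by the full amount of the fall, and it loses or reverses its sign only when the fall reaches the one-year gain. The documents do not support saying that this will happen, or that it is the more probable result.

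This is a secondary outcome. The change is worth making because it replaces an open choice with a better method at little cost, not because the trial would then be well powered for slope.

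**What to change.** Before unblinding, add to the Statistical Analysis section:

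- eGFR is calculated by the 2021 CKD-EPI creatinine equation, as for eligibility.
- One linear mixed model is fitted with eGFR at months 3, 6, 9 and 12 as responses, baseline eGFR as covariate only, and treatment, time and treatment by time as fixed effects. Patient-level random intercept and slope would match the variance terms used above.
- Three differences are reported with 95% confidence intervals: the baseline-adjusted total difference at month 12; the difference at month 3, described as any early fall plus three months of slope; and the difference in slope from month 3 to month 12.
- Progression is interpreted from the total and the slope together, with neither decisive alone.
- A null slope result is not read as absence of effect; the interval is to be discussed.

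The cost is SAP text and one model in the same software, with no new visits, patients or assays. The trade-off is precision: the slope SE is about 1.2-1.6 per year, against 1.0-1.4 for unadjusted 12-month change under the same assumed SDs, which is about 18% larger (√1.4 = 1.18). The early fall cannot be isolated without a visit before month 3, so the report should not claim to have done so.
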